5.0 STUDY PROCEDURES TABLE

Table 5-1: Study Procedures

STUDY PROCEDURES	Screening ^{2,10}	Induction ¹⁵ (7 days)	Cycle 1-4 (Cycle=28 days)		Cycle 5+ (Cycle = 28 days)	End of Treatment ¹³ ± 7 days	Follow Up ¹⁶
			D1	D1 (±3 day)			
Study window							
Informed Consent ¹	X						
Medical history	X				X		
Physical Exam	X	X	X	X	X	X	
Vital signs ³	X	X	X	X	X	X	
ECOG PS	X	X	X	X	X	X	
AE reporting		X	X	X	X	X	X
Concomitant Medications	X	X	X	X	X	X	
Chemistry panel ⁴	X	X	X	X	X	X	
CBC with differential ⁵	X	X	X	X	X	X	
Pregnancy test ⁶	X		X				X
Thyroid function test ⁷	X						
ECHO/ECG	X ¹⁷						
Imaging (CT or MRI) ⁸	X		X ⁸		X ⁷		
Biopsy tissue ^{9,14}	X						
Blood biomarker ¹⁴		X	X ¹⁴				X
Nivolumab infusion ¹¹			X ¹¹	X ¹¹	X ¹¹		
Metformin dispensing ¹²		X	X		X		
Survival							X

1. Informed consent must be signed within 30 days of registration. If signature is outside that window a new consent should be signed.
2. Pre-study H&P and all labs must be ≤ 14 days before registration. Tumor measurements and radiologic evaluations must be ≤28 days before registration.
3. Vital signs include pulse, blood pressure, and weight. Height will be recorded at baseline only.
4. Serum Chemistry will include calcium, chloride, magnesium, phosphorus, creatinine, sodium, potassium, blood urea nitrogen, bicarbonate, glucose, total bilirubin, aspartate aminotransferase (AST), alanine aminotransferase (ALT), alkaline phosphatase (ALP), albumin, and total protein.
5. CBC: Performed at each study visit, prior to nivolumab. For patients experiencing significant drop in WBCs or platelets felt related to treatment, CBCs should be obtained more frequently (weekly or more frequently) to assess timing for retreatment or need for transfusion support.

6. Serum or urine test only for women of childbearing potential; must be tested within 7 days prior to registration and on Cycle 1 Day 1 (prior to nivolumab).
7. Thyroid function tests will include thyroid stimulating hormone and free T4. This will be done at baseline then only as clinically indicated thereafter.
8. The same modality used at baseline should be used throughout for imaging. CT imaging with contrast will occur every 2 cycles starting with Cycle 3 Day 1 (\pm 7 days) and should include chest, abdomen, and pelvis. Neck will be included only if measurable lesions are present. Metformin should be held prior to scans per each institutional protocol. Tumor measurements will be performed using RECIST 1.1. Progressive Disease (PD) must be confirmed by repeat scan within 8 weeks at least after 4 weeks. Patients with a known history of CNS disease must have CNS imaging at screening to rule out activity.
9. Patients will undergo a fresh tissue biopsy prior to study enrollment, unless deemed to be clinically inappropriate per PI. If not feasible, archived tissue will be used (if available).
10. The maximum time interval between registration and the first dose of study drug will be 14 days
11. Nivolumab will be given as follows:
Cycle 1-4: 240mg IV over 30 minutes (-5 / +15 minutes) every 14 days (Day 1 & 15, \pm 3 days)
Cycle 5+: 480mg IV over 60 minutes (-10 / +15 minutes) every 28 days (Day 1, \pm 3 days) until disease progression, intolerance, or withdrawal of consent.
12. Metformin will be dispensed Day 1 of each cycle. Dosing will begin at 1,000mg po once daily and escalate by 500mg every 7 days until the final dose of 2,000mg is reached. Patients will return unused drug and drug bottles at each study visit and will maintain a drug diary to track compliance.
13. The end of treatment visit should occur 30 days after the last dose of study treatment (+/- 7 days) or before starting another line of treatment, whichever comes first.
14. Correlatives from peripheral blood will be collected for all patients at Induction Day 1, C1D1, C3D1, and at the EOT. Biopsy samples (fresh or archived) will be collected for all patients if possible. See separate lab manual for specifications. See section 9.0 for details.
15. Metformin monotherapy will be given at 1,000mg PO QD during the 7-day Induction period, prior to starting nivolumab on Cycle 1 Day 1.
16. After patients come off treatment they will be followed up at 3, 6, 9, and 12 months (\pm 7 days) and then every 6 months (\pm 14 days) for 3 years for survival and progression of disease via either clinic visits or phone calls.
17. Echocardiogram and/or ECG should be performed at screening as clinically indicated for patients with a history of congestive heart failure or at risk because of underlying cardiovascular disease or exposure to cardiotoxic drugs. Cardiac toxicities should be closely monitored throughout treatment.

6.0 ENDPOINT ASSESSMENT

6.1 Solid Tumors

- 6.1.1 Response will be evaluated using the modified Response Evaluation Criteria in Solid Tumors, based on RECIST v1.1.¹²
- 6.1.2 Clinical evaluation and tumor assessments will be performed as indicated in Table 7, based on physical examination and radiologic evaluation.
- 6.1.3 Any lesion that has been previously treated with radiotherapy should be considered as a non-target lesion. However, if a lesion previously treated with radiotherapy has clearly progressed since the radiotherapy, it can be considered as a target lesion.
- 6.1.4 Definitions for measurable and non-measurable lesions, and criteria for response, should be based on RECIST v1.1.
- 6.1.5 **Measurable Lesions**
Must be accurately measured in at least one dimension (greatest diameter) with a minimum size of 10mm by CT scan (cuts of 5mm or less), MRI, or physical exam (ideally using calipers). Bone only disease is allowed, however, must have an osteoblastic component that can be easily measured.
- 6.1.6 **Non-measurable Lesions**
Defined as all other lesions less than 10mm. Examples of non-measurable lesions include leptomeningeal disease, ascites, pleural/pericardial effusions, inflammatory breast disease, lymphangitic involvement of skin or lung.
- 6.1.7 **RECIST Response criteria (used for patient evaluation and treatment decisions)**
 - **Complete Response** - Disappearance of all lesions.
 - **Partial Response** - At least a 30% decrease in the sum of the diameters of target lesions, taking as reference the baseline sum diameters.
 - **Objective Response Rate** – the sum of complete responses and partial responses
 - **Progressive Disease** - At least a 20% increase in the sum of diameters of target lesions, taking as reference the smallest sum on study (this includes the baseline sum if that is the smallest on study). In addition to the relative increase of 20%, the sum must also demonstrate an absolute increase of at least 5 mm. (Note: the appearance of one or more new lesions is also considered progression.)
 - **Stable Disease** - Neither sufficient shrinkage to qualify for PR nor sufficient increase to qualify for PD, taking as reference the smallest sum of diameters while on study.

6.2 Immune-related RECIST (irRECIST)

- 6.2.1 In addition to above, tumor response will be assessed by the irRECIST for investigational purposes, not assessment of primary objective or treatment decisions.¹³ In RECIST v1.1, the appearance of new lesions indicates PD. However, in irRECIST, new measurable lesions are incorporated in the tumor burden, which is used to determine irPD, immune-related partial response (irPR), and immune-related complete response (irCR). New nonmeasurable lesions preclude irCR. Under RECIST v1.1, there is no confirmation for PD. Under irRECIST, responses and irPDs must be confirmed by consecutive scans at least 4 weeks apart, assuming no clinical deterioration. We will define immune-related clinical benefit rate as immune-related stable disease (irSD), irPR, or irCR.

NU Study Number: NU 16L04
Other Study Number: CA 209-801

Table 6-1: Immune-related Response Evaluation Criteria: Overall Response

Tumor Burden (Baseline and New)	Non-Target Lesions (Baseline and New)	Response
Disappearance of non-nodal lesions. All pathologic lymph nodes <10 mm (short axis)	Disappearance of non-nodal lesions. All pathologic lymph nodes < 10 mm (short axis)	irCR
≥30% decrease from baseline	Any	irPR
≥20% increase from nadir and at least 5 mm	Any	irPD
Neither sufficient decrease to qualify for PR, nor sufficient increase to qualify for PD	Any	irSD
Disappearance of all non-nodal lesions. All pathologic lymph nodes <10 mm	Any other than disappearance of all non-nodal lesions and reduction of pathologic lymph nodes <10 mm	irPR
Not all evaluated	Any	irNE

irCR = immune-related complete response; irPD = immune-related progressive disease; irPR = immune-related partial response; irNE = immune-related not evaluable; irSD = immune-related stable disease;

-Tumor burden is the sum of single diameters (short axis for nodal lesions, longest diameter for other lesions) for the target lesions. In subsequent scans, the diameters of new measurable lesions are added to the tumor burden.

-Best overall response based on 2 consecutive measurements at least 4 weeks apart.

6.3 Primary Endpoint

To assess anti-tumor activity of the combination treatment of nivolumab and metformin in patients with advanced non-small cell lung cancer: Anti-tumor activity will be assessed by objective response rate (ORR, complete response and partial response) using RECIST criteria. All patients who receive treatment will be considered evaluable except those removed from the study for adverse drug reactions.

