4.3.2 Treatment discontinuation: nivolumab

Should the treating physician decide to discontinue treatment given suspicion for a drug-related side effect, the side effect should be attributed to one study drug to the best of the physician's ability. Nivolumab should be discontinued based on this attribution, and the patient must come off study treatment. The patient may not receive metformin monotherapy on-study.

Nivolumab should be discontinued permanently for the following:

- Any Grade 2 drug-related uveitis, eye pain, or blurred vision that does not respond to topical therapy and does not improve to Grade 1 severity within the re-treatment period OR requires systemic treatment
- Any Grade 3 non-skin, drug-related adverse event lasting > 7 days, with the following exceptions for laboratory abnormalities, drug-related uveitis, pneumonitis, bronchospasm, hypersensitivity reactions, infusion reactions, and endocrinopathies:
 - Grade 3 drug-related uveitis, pneumonitis, bronchospasm, hypersensitivity reaction, or infusion reaction of any duration requires discontinuation
 - Grade 3 drug endocrinopathies adequately controlled with only physiologic hormone replacement do not require discontinuation
 - Grade 3 drug-related laboratory abnormalities do not require treatment discontinuation except:
 - Grade 3 drug-related thrombocytopenia > 7 days or associated with bleeding (aside from minor bleeds \leq Grade 1) requires discontinuation
 - Any drug-related liver function test (LFT) abnormality that meets the following criteria require discontinuation:
 - AST or ALT $> 5-10 \times$ ULN for > 2 weeks
 - AST or ALT $> 10 \times$ ULN
 - Total bilirubin $> 5 \times$ ULN
 - Concurrent AST or ALT $> 3 \times$ ULN and total bilirubin $> 2 \times$ ULN
- Any Grade 4 drug-related adverse event or laboratory abnormality, except for the following events which do not require discontinuation:
 - Grade 4 neutropenia < 7 days
 - Grade 4 lymphopenia or leukopenia
 - Isolated Grade 4 amylase or lipase abnormalities that are not associated with symptoms or clinical manifestations of pancreatitis. PI and Data and Safety Monitoring Committee (DSMC) should be consulted for Grade 4 amylase or lipase abnormalities.

NU Study Number: NU 16L04
Other Study Number: CA 209-801

- Isolated Grade 4 electrolyte imbalances/abnormalities that are not associated with clinical sequelae and are corrected with supplementation/appropriate management within 72 hours of their onset

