4.3.4 Metformin

The most common adverse reactions to metformin are diarrhea, nausea/vomiting, flatulence, indigestion, and headaches. These side effects occur most commonly upon initiation of therapy and are short lived. These effects are mitigated by dose escalation regimens that are used in this trial. Dose reduction or discontinuation will be applied in patients with persistent gastrointestinal symptoms related to metformin. A rare but serious side effect of metformin is lactic acidosis, which is most common in patients with renal insufficiency and congestive heart failure. Lactic acidosis can be evaluated by checking a patient's renal function in addition to their serum lactic levels. Any clinical or laboratory indication of metabolic acidosis will lead to immediate discontinuation of metformin.

For commonly observed gastrointestinal AEs of metformin such as nausea, vomiting and diarrhea the dose should be withheld. Metformin should be held until the AE resolves to \leq Grade 1 or baseline and restarted at a lower dose level as per Table 4-3. Metformin can be held for a maximum of 28 days. Patients who permanently discontinue metformin for toxicity must come off study treatment – they may not receive nivolumab monotherapy on-study.

Metformin-induced side effects as determined by the study investigator should be managed as listed below in tables 4-3 and 4-4.

Table 4-3: Metformin-related toxicity dose reductions	
CTCAE Grade	Metformin Dosing
0-2	No change from original starting dose
3 (1 st occurrence)	Hold until resolved to \leq grade 1 or baseline, then reduce to lower dose
3 (2 nd occurrence)	Hold until resolved to \leq grade 1 or baseline, then reduce to lower dose
3 (3 rd occurrence) or 4	Discontinue treatment

Table 4-4: Dose reduction of Metformin for toxicity	
Current dose	Reduced dose
2000 mg	1500 mg
1500 mg	1000 mg
1000 mg	500 mg
500 mg	Discontinue*

Note: For the purpose of imaging with CT scan with IV contrast, metformin can be held according to the institution's CT scan protocol.

*Patients will discontinue all study treatment

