4.7 Duration of Follow Up

All patients will be followed for adverse events for 30 days after last dose of study treatment (100 days for SAEs), or until the patient starts a new treatment, whichever occurs first. Patients who discontinue treatment for unacceptable adverse event(s) will be followed until resolution or stabilization of the adverse event (i.e. the grade is not changing). If a patient stops treatment due to unacceptable adverse event(s) but has not demonstrated disease progression, then the patient will be followed with imaging studies every 8 weeks until the time of progression radiographically according to RECIST 1.1 criteria. In the event that a radiographic response is detected, then this event will be included as a response in the final analysis, and the time of progression used in calculation of the survival analysis. Patients will be followed for survival status every 3 months for 1 year and every 6 months for a total of 3 years after treatment discontinuation for survival or progression of disease.

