4.8 Removal of Subjects from Study Treatment and/or Study as a Whole

Patients can be taken off the study treatment and/or study as a whole at any time at their own request, or they may be withdrawn at the discretion of the investigator for safety, behavioral or administrative reasons. The reason(s) for discontinuation must be clearly documented on the appropriate eCRF and may include:

- Patient voluntarily withdraws from treatment (follow-up permitted)

NU Study Number: NU 16L04
Other Study Number: CA 209-801

- Patient withdraws consent (no follow-up permitted)
- Patient is unable to comply with protocol requirements
- Patient demonstrates disease progression
- Patient experiences unacceptable toxicity
- Treating physician determines that continuation on the study would not be in the patient's best interest
- Patient becomes pregnant
- Patient develops a second malignancy that requires treatment which would interfere with this study
- Patient becomes lost to follow-up (LTf)

Patients who are permanently discontinued from receiving investigational product will be followed for disease progression and safety, including the collection of any protocol-specified blood specimens, unless consent is withdrawn or the subject is lost to follow-up or administered subsequent therapy. All subjects will be followed for survival and disease progression. Subjects who decline to return to the site for evaluations will be offered follow-up by phone every 3 months as an alternative.

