10.3 Data Analyses Plans

Summary of Analytic plan for primary objective	Summary of Analytic plan for secondary objectives

Please refer to the below sample size justification for the parallel Simon's two stage design which defines how the endpoints are met.
 
For Group A. Estimated ORR for historical control is 20% versus target ORR of 40% for nivolumab and metformin combination treatment.
	
Depth of response: waterfall plot Duration and persistence of response: swimmer's plot PFS: PFS at 1 and 2 years (Kaplan-Meier analysis) OS: OS at 1 and 2 years (Kaplan-Meier analysis) ORR, DCR by irRC (descriptive statistics,

NU Study Number: NU 16L04
Other Study Number: CA 209-801

For Group B. Estimated ORR for refractory patients is 5% versus target ORR of 40% for niovulomab and metformin combination treatment.
	
exact binomial confidence intervals) We will use descriptive statistics and graphical displays to evaluate change in serum biomarkers between pre- and post-treatment. A Wilcoxon signed rank test will be used to determine if there is a statistically significant change in serum biomarkers. Toxicities will be tabulated by type and grade.

--	---

The primary analysis will be on the evaluable analysis set, including all evaluable patients regardless of drug exposure. Clinical benefit rate will be defined as stable disease (for ≥ 12 weeks), complete or partial response by both the Response Evaluation Criteria in Solid Tumors (RECIST) and irRECIST. Maximum response prior to disease progression will be used. The overall response rate will be estimated by the proportion of overall response, and its 80% confidence interval (CI) and 95% CI will be estimated using the exact binomial distribution.

Additionally, we will evaluate overall response rate, defined as complete or partial response using RECIST guidelines in a similar manner. We will also perform similar analyses using Immune Related RECIST (irRECIST). Duration of response, defined as the duration from the first documentation of clinical benefit to the first documented progressive disease or death of any cause, whichever occurs first, will also be analyzed. For patients alive and progression-free at the time of data cut off, duration of response will be censored as of the last tumor assessment date. Duration of response will only be evaluated for the subgroup of patients with a clinical benefit using the Kaplan-Meier method.

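### Section 6.3 drops treated patients removed for adverse drug reactions from the primary ORR set and never counts them as non-responders, so the reported ORR can be biased upward

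*Combined protocol and SAP*

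**What the plan says.** Section 6.3 (Primary Endpoint) gives the only definition of evaluable for response: "All patients who receive treatment will be considered evaluable except those removed from the study for adverse drug reactions". Section 10.3 then states: "The primary analysis will be on the evaluable analysis set, including all evaluable patients regardless of drug exposure". The closing words of that sentence take the evaluable set as given and do not bring back the patients whom 6.3 removes. Section 10.3 adds that, for the response rate, "its 80% confidence interval (CI) and 95% CI will be estimated using the exact binomial distribution".

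Four other sections bear on patients who stop for toxicity:

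- **4.3.2 and 4.3.4** speak of treatment, not of the study: "Nivolumab should be discontinued based on this attribution, and the patient must come off study treatment" and "Patients who permanently discontinue metformin for toxicity must come off study treatment".
- **4.7** says that if such a patient has not progressed, "the patient will be followed with imaging studies every 8 weeks until the time of progression". It continues: "In the event that a radiographic response is detected, then this event will be included as a response in the final analysis". It has no matching sentence for those who never respond.
- **4.8** lists unacceptable toxicity under the heading "Removal of Subjects from Study Treatment and/or Study as a Whole", and also says that all subjects are followed for progression.
- **4.9** provides for replacement only when a patient comes off study before Cycle 1 Day 1. Section 10.2 sets accrual at 51 for 49 evaluable patients, to allow for inevaluable patients and dropout.

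**The concern.** The exclusion depends on a post-treatment outcome. For anti-tumour activity, a treated patient who leaves for toxicity without a response is a failure. Under 6.3 that patient is not counted at all. The ORR then describes patients who tolerated the regimen, yet readers will set it and its exact intervals against a fixed historical rate. Section 8.3.1 says that no trial of this combination has been reported, so the number of patients affected cannot be known in advance.

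The wording also has two possible reaches. If removal means leaving the study altogether, few patients are affected, but selection still depends on outcome. If it also covers stopping treatment, 4.7 makes it one-directional: patients who stop for toxicity and respond enter the numerator, and those who do not respond leave the denominator.

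**Working it through.** Designs are labelled by their rates, because Section 1.3.2 and Section 10.2 attach them to opposite arms. That is a separate point.

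**Inputs (Section 10.2).** 5%/20% design: n1 = 9, stop if 0 responses; n = 24, pass at 3 or more. 20%/40% design: n1 = 12, stop if 2 or fewer; n = 25, pass at 8 or more. Nominal type I error is 10% and power 80%. The allowance is 51 − 49 = 2 patients (2/51 = 3.9%). The number of patients removed is an assumption throughout.

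**1. Reproducing the plan's designs.** With stage-1 bound r1 and final bound r, P(pass | p) = Σ over x from r1+1 to n1 of b(x; n1, p) × P(Y ≥ r+1−x), where Y ~ Bin(n−n1, p).

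| Design | Type I error at null | Power at target | Early stop at null |
|---|---|---|---|
| 5%/20% | 0.093 | 0.805 | 0.630 |
| 20%/40% | 0.099 | 0.815 | 0.558 |

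These agree with the stated limits and with the stated 63% and 56%, each taken at its own null rate.

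**2. Effect on the reported ORR, fixed cohort.** If k non-responders are dropped, x/n becomes x/(n−k), a relative rise of n/(n−k) − 1. Exact limits are beta quantiles: lower Beta(α/2; x, n−x+1), upper Beta(1−α/2; x+1, n−x).

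| Case | ORR | 80% CI | 95% CI |
|---|---|---|---|
| 8/25 | 32.0% | 19.6–46.7 | 15.0–53.5 |
| 8/24 (k = 1) | 33.3% | 20.5–48.4 | 15.6–55.3 |
| 3/24 | 12.5% | 4.7–25.8 | 2.7–32.4 |
| 3/23 (k = 1) | 13.0% | 4.9–26.8 | 2.8–33.6 |
| 3/22 (k = 2) | 13.6% | 5.1–27.9 | 2.9–34.9 |

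Relative rises: 25/24 = 1.042, or 4.2%; 24/22 = 1.091, or 9.1%. The 80% lower limit passes the null rate with one exclusion in the 20%/40% design and with two in the 5%/20% design. The 95% lower limits stay below the null rates.

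**3. Effect on the decision rule.** Without refilling, dropping non-responders leaves the response count unchanged, so type I error stays at 0.099 and 0.093. If a fraction f of entrants are non-responders who are dropped and refilled, the evaluable response rate is p/(1−f). For f = 2/51, 0.20/(49/51) = 0.2082 and 0.05/(49/51) = 0.0520. Putting these rates into the formula of step 1:

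| f (assumed) | 20%/40% design | 5%/20% design |
|---|---|---|
| 0 | 0.099 | 0.093 |
| 1/51 | 0.108 | 0.097 |
| 2/51 | 0.119 | 0.102 |
| both spares in this arm (2/27 or 2/26) | 0.140 | 0.111 |

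In the last row the other arm keeps its value at f = 0.

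**The case against.** **Reach.** The document largely handles the common case. Toxicity ends study treatment, not participation. Section 4.7 keeps imaging patients who have not progressed, and someone imaged to progression without a CR or PR is an observed non-responder who needs no imputation. This stands as far as it goes: the text favours the off-study reading, on which few patients are excluded. It does not settle the matter, because the heading of 4.8 covers both treatment and study, and no sentence puts the non-responders back into the denominator.

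**Direction.** Read literally, 6.3 drops responders and non-responders alike. Dropping one responder would turn 8/25 into 7/24 = 29.2% and a pass into a fail. If removal were unrelated to response, the expected bias would be zero. That is correct, and it is why the claim is that the ORR can be, not will be, biased upward. The bias is upward when removed patients respond less often, or when 4.7 retains only the responders.

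**Size.** The shifts are 1.3 and 1.1 percentage points, against 80% intervals more than 20 points wide. No CI limit is a decision criterion, and the exclusion counts shown are the smallest that carry the 80% lower limit past the null. All of this stands. The crossing shows how little is needed to change how a boundary result reads; it does not change the trial's decision.

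**Refilling.** Section 4.9 offers replacement only before Cycle 1 Day 1, which argues against refilling later. It does not forbid it, and the two-patient allowance is there for inevaluable patients.

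**Conclusion.** The concern holds. The primary ORR is taken on a set that leaves out treated patients because of toxicity after treatment began. No rule counts them as non-responders, and no all-treated ORR is planned. Following the plan as written can therefore give an inflated estimate.

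The size is modest and conditional. At the pass boundary the ORR rises by 4.2% in relative terms with one dropped non-responder of 25, and by 9.1% with two of 24. This assumes that the dropped patients are non-responders. The go/no-go rule is not inflated unless they are refilled; at assumed rates up to 2/51 the type I error then reaches 0.119 and 0.102 against the nominal 0.10. This should be fixed, but it does not undermine the design.

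**What to change.** 1. In 6.3, delete the exception for adverse drug reactions.
2. In 10.3, define the primary analysis set as all patients who receive study treatment, leaving out only those replaced under 4.9 before Cycle 1 Day 1. Count everyone without a documented CR or PR as a non-responder, including toxicity removals and patients with no post-baseline scan.
3. State that patients removed for toxicity after Cycle 1 Day 1 are not replaced.
4. Keep the present evaluable set as a sensitivity analysis, and say there whether removal means off study only.
5. List patients replaced after induction metformin, with reasons. As a further sensitivity analysis, report the ORR with them counted as non-responders. They have received study treatment, so leaving them out of the primary set should be visible. Section 4.9 itself need not change.

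The cost is wording in 6.3 and 10.3 plus one sentence on replacement. No patients are added, no treatment rule changes, and the Simon error rates stay at 0.099 and 0.093. The reported ORR may be slightly lower.
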